8.8 Management Following Relapse

Management following relapse is at the discretion of the investigator. Survival and protocol chemotherapy or surgery related adverse events data should continue to be capture after first relapse.

9.0 SERIOUS ADVERSE EVENT REPORTING

The descriptions and grading scales found in the NCI Common Terminology Criteria for Adverse Events (CTCAE) will be utilized for Adverse Event (AE) reporting (version can be found in Appendix III). All appropriate treatment areas should have access to a copy of the CTCAE. A copy of the CTCAE can be downloaded from the CTEP web site: (http://ctep.cancer.gov/protocolDevelopment/electronic_applications/ctc.htm).

All serious adverse events (SAE) defined as per ICH guidelines (see below) and other adverse events must be recorded on case report forms. In addition, all “reportable” serious adverse events are subject to expedited reporting using the CCTG SAE form. The term ‘reportable SAE’ is used in the definitions which follow to describe those SAEs which are subject to expedited reporting to CCTG.

9.1 Definition of a Reportable Serious Adverse Event

- All serious adverse events, which are unexpected and related to protocol treatment must be reported in an expedited manner (see Section 9.2 for reporting instructions). These include events occurring during the treatment period (until 30 days after last protocol treatment) and at any time afterwards.
- Unexpected adverse events are those, which are not consistent in either nature or severity with information contained in the product monograph.
- Adverse events considered related to protocol treatment are those for which a relationship to the protocol agent cannot reasonably be ruled out.
- A serious adverse event (SAE) is any adverse event that at any dose:
 - results in death
 - is life-threatening
 - requires inpatient hospitalization or prolongation of existing hospitalization (excluding hospital admissions for study drug administration, transfusional support, scheduled elective surgery and admissions for palliative or terminal care)
 - results in persistent or significant disability or incapacity
 - is a congenital anomaly/birth defect

Medical and scientific judgement should be exercised in deciding whether expedited reporting is appropriate in other situations such as important medical events that may not be immediately life-threatening or result in death or hospitalization but may jeopardize the patient or may require intervention to prevent one of the events listed above.

9.2 Serious Adverse Event Reporting Instructions

All reportable serious adverse events must be reported using a web-based Electronic Data Capture (EDC) system being used for this trial. For details about accessing the EDC system and completing the on-line SAE report form, please refer to the CCTG Generic Data Management Guidebook for EDC Studies posted on the CO.28 section of the CCTG website (www.ctg.queensu.ca).

Within 24 hours: Complete preliminary Serious Adverse Event Report and submit to CCTG via EDC system.

Within 7 days: Update Serious Adverse Event Report as much as possible and submit report to CCTG via EDC system.

EDC SAE web application interruption:

In the rare event that internet connectivity to the EDC SAE system is disrupted, please print and complete a paper copy of the SAE Report, available from the trial specific website.

FAX paper SAE Report to:

CO.28 Study Coordinator
Canadian Cancer Trials Group
[contact]

Please use the same timelines for submission as for direct EDC reporting.

Once internet connectivity is restored, the information that was FAXED to CCTG on the paper SAE Report must also be entered by the site into the EDC SAE web application.

Local internet interruption:

If you are unable to access the EDC SAE system, and cannot access a paper copy of the SAE Report from the trial website, please phone the CO.28 trial team [contact]) to obtain a copy of the SAE Report by FAX. Once completed, the report must be FAXED back to CCTG as indicated above. Once internet connectivity is restored, the information that was FAXED to CCTG on the paper SAE Report must also be entered by the site into the EDC SAE web application.

In cases of prolonged internet interruptions, please contact the CCTG Safety Desk for further instructions [contact]).

9.3 Other Protocol Reportable Events – Pregnancy Reporting and Exposure Reporting

9.3.1 Pregnancy Prevention

Women of Childbearing Potential (WOCBP) and males who are enrolled in the trial must have agreed to use contraceptive method(s) as described in Eligibility Criterion 4.1.15. Investigators may wish to additionally advise the female partners of male participants about pregnancy prevention guidelines when appropriate and compliant with local policy.

9.3.2 Pregnancy Reporting

The investigator is required to report to CCTG any pregnancy occurring in female participants, and female partners of male participants. Pregnancies occurring up to 6 months after the completion of study treatment must also be reported.

The investigator should report the pregnancy in a timely manner, within 24 hours of learning of the pregnancy using the CCTG Pregnancy Reporting Form available from the trial webpage.

Once informed consent has been obtained, the form should be updated to provide further pregnancy information and to reflect the outcome of the pregnancy. All follow-up reports must be submitted to CCTG in a timely manner. For pregnant partner of trial participant (and pregnant participants, if required by local policy), a copy of the signed signature page of the pregnancy follow-up consent must be submitted to CCTG.

Documents outlined above (including updates) must be sent to the CCTG safety desk [contact]/ [contact]).

If the pregnancy results in death (e.g. spontaneous abortion, stillbirth); is life-threatening; requires inpatient hospitalization or prolongation of existing hospitalization; results in persistent or significant disability/incapacity; is a congenital anomaly/birth defect, then an SAE report must be additionally submitted as described above. Please note, hospitalization for labour/delivery alone does not constitute an ‘inpatient hospitalization’ for the purposes of pregnancy reporting.

9.3.3 Exposure Reporting (Non-study Participants)

The investigator is required to report to CCTG any incidence of exposure to study agent(s). Exposure is defined as significant, direct, contact/inhalation/consumption of agent(s) by non-study participant (an individual who is not otherwise participating in this clinical trial). An example of an exposure includes a non-study participant swallowing study medication. The investigator is responsible for determining significance, based on the agent to which the individual is exposed.

The investigator should report the exposure in a timely manner, within 24 hours of learning of the exposure using the CCTG Exposure Reporting Form available from the trial webpage.

Once informed consent has been obtained, the form should be updated to provide further exposure information and to reflect the outcome of the exposure as the information becomes available upon appropriate follow-up of the exposed individual for 30 days after the last dose/exposure. All follow-up reports must be submitted to CCTG in a timely manner. A copy of the signed exposure follow-up consent signature page must also be submitted to CCTG.

Documents outlined above (including updates) must be sent to the CCTG safety desk [contact]/ [contact]).

If the exposure results in death; is life-threatening; requires inpatient hospitalization or prolongation of existing hospitalization; results in persistent or significant disability/incapacity; is a congenital anomaly/birth defect, then an SAE report must be additionally submitted as described above.

9.4 CCTG Responsibility for Reporting Serious Adverse Events to Health Canada

The CCTG will provide expedited reports of SAEs to Health Canada for those events which meet regulatory requirements for expedited reporting, i.e. events which are BOTH serious AND unexpected, AND which are thought to be related to protocol treatment (or for which a causal relationship with protocol treatment cannot be ruled out).

9.5 Reporting Safety Reports to Investigators

CCTG will notify Investigators of all Safety Reports (Serious Adverse Events (SAEs) from this trial and Safety Updates (SUs) single reports or line listings) from other clinical trials that are reportable to regulatory authorities in Canada as reported to the CCTG. This includes all serious events that are unexpected and related (i.e. possibly, probably, or definitely) to protocol treatment. The reports will be posted to the CCTG trial CO.28 web-based safety monitoring utility. Investigators must review and document in the trial files proof of review of these events as per ICH GCP.

Investigators must notify their Research Ethics Boards (REBs) of events, which involve corrective action(s) to be taken as a result of the event(s) such as protocol and/or informed consent changes and any other event required by their REB. Safety reports that are not mandated by CCTG to be submitted to the REB are marked as 'NR' (not required) in the safety report monitoring utility. The date of REB Submission for these SAEs and SUs will need to be entered into the CCTG trial CO.28 web based safety monitoring utility and documentation of REB submission must be retained in the study binder on site. The REB submission template provided by CCTG can be used to assist with tracking, submission, filing and monitoring.

The submission of events to your ethics board should be done as soon as possible (we suggest within 30 days). REB submissions greater than 90 days from the date of notification will be regarded as delinquent and a major deficiency will be assigned. These safety reports are to be filed in the trial files on site.

10.0 PROTOCOL TREATMENT DISCONTINUATION AND THERAPY AFTER STOPPING

10.1 Criteria for Discontinuing Protocol Treatment

Patients may stop protocol treatment in the following instances:

- Intercurrent illness which would, in the judgement of the investigator, affect assessments of clinical status to a significant degree, and require discontinuation of protocol therapy.
- Unacceptable toxicity as defined in Section 7.0.
- Tumour progression as defined in Section 8.2.
- Request by the patient.
- Completion of therapy as outlined in Section 7.0.

Efforts should be made to maintain the investigations schedule and continue follow-up, even if patients discontinue protocol treatment prematurely and/or no longer attend the participating institution.

10.2 Therapy After Protocol Treatment

Supportive care therapy is recommended as per local standards.

10.3 Follow-up Off Protocol Treatment

All patients will be seen 30 days after excision and then at months 6, 12, 18, 24, 30, 36, 48 and from the excision date (please refer to section 5.0 for more details). Phone contacts at months 48 and 60 after excision will be acceptable.

11.0 CENTRAL REVIEW PROCEDURES

11.1 Retrospective ypstaging Central Pathology Review

There will be central pathology review for this study. Expert retrospective pathology review will be done for all patients to confirm ypstaging after excision. At least one disease site specialty pathologist with recognized diagnostic expertise for the tumour type will review the specimens and pathology report of each case. Another expert pathologist will be consulted to resolve significant diagnostic discordance if it arises. Results of the central pathology review will not be provided to the originating institution, the patient or patient record. Please consult CO.28 Correlative Studies Manual for additional details and timelines.

11.2 Central Surgery Review

Surgeons performing TEMS/TAMIS in this trial should have performed these procedures in at least 20 previous rectal cancer cases *[Stevenson, 2015; Bonjer, 2015; Fleschman, 2015]*.

Each surgeon should submit an unedited video of a TEMS/TAMIS procedure with sutured defect closure for central review. A video of the 1st patient enrolled in CO.28 is acceptable.

Please contact CO.28 CCTG Study Coordinator for additional details about video characteristics and its submission for central review.

12.0 CORRELATIVE STUDIES

A detailed Correlative Studies Manual will be provided on the CO.28 trial specific website, which will include details regarding sample preparation, handling and shipping.

Specimens collected may be used by researchers now or in the future to better understand the nature of rectal cancer and how patients respond to treatment. Samples will be used for research purposes only and will not be sold. Patients will not be identified by name. The only identification of tissue will be by a patient study number assigned at the time of enrollment to the trial the surgical/ histology number and/or patient initials. Material issued to researchers will be anonymized and only identified by a coded number.

Testing for hereditary genetic defects predisposing to malignant disease will not be carried out without the expressed consent of the patient.

All patients on whom a diagnostic tumour block or slides are collected will be aware of this retrieval and will have given their consent.

12.1 Protocol-Mandated Correlative Studies

Tumour Tissue Collection

Consenting to submit representative tumour tissue of the diagnostic tumour tissue from a biopsy done prior to enrollment AND from the protocol excision that removes the primary tumour is mandatory for participation in this trial.

One formalin fixed paraffin embedded (FFPE) block and one adjacent normal tissue block are requested from both the diagnostic tumour tissue from a biopsy done prior to enrollment AND from the protocol excision that removes the primary tumour. Where local centre regulations prohibit submission of tissue blocks, sites should request approval from the CCTG prior to local site activation to permit cores (2 x 2 mm cores of tumour) and slides (20 X 5 micron thick unstained slides from the block) to be submitted as an alternative to a block of tumour tissue. If, at any time, the submitting hospital requires the block or slides to be returned for medical or legal concerns, it will be returned by courier on request.

Whole blood (for ctDNA), Whole Blood, Serum and Plasma Collection

The submission of whole blood (for ctDNA), whole blood, serum and plasma is mandatory for participation in this trial.

The CCTG is interested in exploring the use of surrogate tissues such as serum and plasma in evaluating potential prognostic or predictive biomarkers, or as evidence of pharmacodynamic effects. Whole blood, serum and plasma will be collected from all patients for planned studies for this trial.

Planned priority assay:

- Circulating tumour DNA

Detailed instructions for whole blood (for ctDNA), whole blood, serum and plasma sample acquisition, preparation, and shipping are found in the CO.28 Correlative Studies Manual.

12.2 Optional Banking of Samples

Banking of Tumour Tissue

Mandatory submission of tumour tissue has been described above. The subsequent banking of any remaining diagnostic tissue collected is not mandatory for participation in the study, but the participation of all centres is strongly encouraged. Blocks will be carefully banked as part of the CCTG tissue/tumour bank at Queen's University in Kingston, Ontario.

Proposals to use the banked specimens for the purposes of assessing markers involved in predicting treatment response and outcomes may be submitted to the bank. A scientific review process of any proposals to use the tissue will take place and any proposals approved will have undergone ethics approval.

Banking of Whole Blood, Serum and Plasma

Mandatory submission of whole blood, serum and plasma has been described above. The subsequent banking of any remaining blood samples collected is not mandatory for participation in the study. Blood samples will be carefully banked as part of the CCTG tissue/tumour bank at Queen's University in Kingston, Ontario.

Proposals to use the banked specimens for the purposes of assessing markers involved in predicting treatment response and outcomes may be submitted to the bank. A scientific review process of any proposals to use the tissue will take place and any proposals approved will have undergone ethics approval.

13.0 STATISTICAL CONSIDERATIONS

13.1 Objectives and Design

This is a single-arm two-stage trial with the primary objective to determine the organ preservation rate in patients with early (cT1-3a,bN0) rectal cancer treated with neoadjuvant FOLFOX or CAPOX and TEMS or TEMIS. Secondary objectives include estimation of 3 year locoregional relapse rate, distant relapse rate, and disease free survival in patients treated with organ preservation and evaluation of toxicities and quality of life.

13.2 Endpoints and Analysis

The primary endpoint of this study is the protocol specified organ preservation rate, defined as the proportion of patients with tumour downstaging to $ypT0/T1^{good}$ N0 and who avoid radical surgery. The 95% confidence interval for the organ preservation rate will be calculated.

The 3 year locoregional relapse rate, distant relapse rate, and disease free survival will be estimated based on Kaplan-Meier method.

13.3 Sample Size and Duration of Study

Prospective phase II studies have documented an organ preservation rate of 50-68% among patients with clinical T1-3N0 rectal tumours treated with chemoradiation and minimally invasive surgery.

Based on these historic phase II data, the experimental treatment would be considered of no interest if the protocol specified organ preservation rate is 50% or lower (H_0) and as promising if its avoidance rate is 65% or higher (H_1). With an optimal two-stage minimax design, 22 patients would be accrued in the first stage.

The trial would be stopped at the end of the first stage if the number of patients who avoided radical surgery is 10 or less. Otherwise the trial would proceed to the second stage to accrue 28 additional patients. The experimental procedure would be considered as promising if, out of the total patients accrued, 30 or more patients avoided radical surgery. The exact type I error rate and power of this design are respectively 0.1 and 0.8. The minimum and maximum sample sizes are respectively 22 and 50 evaluable patients. Allowing for a 15% inevaluable rate, the total sample size is 58 patients.

The interim analysis at 22 patients will also determine if the trial has recruited a proportional representation of T1/2 and T3 patients. If the interim analysis shows disproportionality between the number of T1/2 and T3 patients, the eligibility criteria and reasons limiting enrollment will be reviewed and the trial team will consider extending accrual of one or the other group if it is determined to be necessary.

If the avoidance rate of the proposed procedure is 50% or lower, there is a 42% chance this study would be stopped.

Based on CCTG previous survey results, the study potentially opening at 12 centres, each centre accruing 3 patients per year, the estimated minimum accrual time for 58 patients is 19 months.

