8.0 CRITERIA FOR MEASUREMENT OF STUDY ENDPOINTS

8.1 Definitions

8.1.1 *Evaluable for Organ Preservation Rate*

All patients treated with FOLFOX or CAPOX and TEMS or TAMIS will be included in the organ preservation rate analysis as primary endpoint of this study.

Organ preservation rate will additionally be calculated for all patients that have received protocol chemotherapy.

8.1.2 *Evaluable for Rectal Cancer Control*

All patients treated with FOLFOX or CAPOX and TEMS or TAMIS will be evaluated for locoregional and distant relapse rate.

Rectal cancer control will additionally be calculated for all patients that have received protocol chemotherapy.

8.1.3 *Evaluable for Disease Free Survival*

All patients treated with FOLFOX or CAPOX and TEMS or TAMIS will be evaluable for assessment of disease free survival.

Disease Free Survival will additionally be calculated for all patients that have received protocol chemotherapy.

8.1.4 *Evaluable for Post-Operative Complications*

All patients treated with FOLFOX or CAPOX and tumour excision/surgery will be evaluable for post-operative complications.

8.1.5 *Evaluable For Adverse Events*

All patients who have received at least one dose of protocol chemotherapy will be included in the safety analysis.

8.1.6 *Evaluable for Quality of Life Assessment*

All patients who have completed a quality of life questionnaire are evaluable for quality of life.

8.2 *Evidence of Disease Progression/No Response After Chemotherapy*

8.2.1 *Progression*

The diagnosis of progressive disease will be made by treating surgeon after review of the pre-excision (post-chemotherapy) MRI and endoscopy.

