2.2 Study Design

CO.28 is a single arm, two-stage phase II clinical study of FOLFOX/CAPOX as a neoadjuvant treatment for patients with stage I-II (cT1-3ab/N0) rectal cancer. The study is being conducted by the Canadian Cancer Trials Group.

A total of 50 evaluable patients would be enrolled, in a two-stage minimax design with 22 patients accrued in the first stage. The trial would be stopped at the end of the first stage if the number of patients who avoided radical surgery is 10 or less. Otherwise the trial would proceed to the second stage to accrue 28 additional patients. Allowing for a 15% inevaluable rate, the total sample size would be 58 patients.

This study opened to accrue patients on August 22, 2017. On April 19, 2019, 11 of the 19 patients enrolled in the first stage were found to have avoided radical surgery. It was decided the study would proceed to continue accrual of patients to full sample size. The trial was closed to further accrual on May 19, 2020 after 58 patients were accrued.

A final analysis will be performed on a database which will be locked after all patients completed their treatments and all data observed from the patients are cleaned. This plan describes the details of this final analysis.

The CCTG Data and Safety Monitoring Committee (DSMC) has been reviewing safety data annually and as otherwise required. These analyses have been prepared by a CCTG/Queen's Senior Biostatistician.

3. Objectives

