4.3 Safety

The safety endpoints are post-operative complication rate, serious and non-serious adverse events (clinical and laboratory), laboratory parameters, dosing data (including dose interruptions, total delivered dose and dose modifications) and reasons off treatment.

5. Sample Size and Power

The expected organ preservation rate is 50-68% among patients with clinical T1-3N0 rectal tumours treated with chemoradiation and minimally invasive surgery. Based on these historic phase II data, the experimental treatment would be considered of no interest if the protocol specified organ preservation rate is 50% or lower (H_0) and as promising if its avoidance rate is 65% or higher (H_1).

An optimal two-stage minimax design would be used to test the above hypotheses, which would accrual 22 evaluable patients in the first stage. The trial would be stopped at the end of the first stage if the number of patients who avoided radical surgery is 10 or less. Otherwise the trial would proceed to the second stage to accrue 28 additional evaluable patients. The experimental procedure would be considered as promising if, out of the total patients accrued, 30 or more patients avoided radical surgery. The exact type I error rate and power of this design are respectively 0.1 and 0.8. Allowing for a 15% inevaluable rate, the total sample size would be 58 patients.

6. Data Set Descriptions

Five types of analysis samples will be used:

1. All Accrued Patients:

All patients accrued in the study.

2. All Chemotherapy Treated Patients:

All patients who have received at least one dose of FOLFOX or CAPOX.

3. All Chemotherapy & Excision Treated Patients

All patients who have received at least one dose of FOLFOX or CAPOX and TEMS or TAMIS.

4. All Chemotherapy & Excision/Surgery Treated Patients

All patients who have received at least one dose of FOLFOX or CAPOX and excision (TEMS or TAMIS) or surgery (TME).

5. All Quality of Life Evaluable Patients

All patients who have completed at least one quality of life questionnaire.

7. Statistical Analysis

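### The final success rule is a fixed count of 30, which meets the stated type I error and power together only at exactly 50 evaluable patients; no rule covers any other number, and section 2.0 states a different threshold

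*Protocol*

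**What the plan says.** Protocol 13.3 sets H0 at an organ preservation rate of 50% or lower and H1 at 65% or higher. The first stage has 22 patients and stops at 10 or fewer successes; otherwise 28 more are accrued. The treatment is then "considered as promising if, out of the total patients accrued, 30 or more patients avoided radical surgery". The stated type I error is 0.1, the power 0.8 and the chance of early stopping under H0 42%. On size, "The minimum and maximum sample sizes are respectively 22 and 50 evaluable patients", and "Allowing for a 15% inevaluable rate, the total sample size is 58 patients".

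SAP section 5 repeats the count ("out of the total patients accrued, 30 or more patients avoided radical surgery") and describes the second stage as a decision to "proceed to the second stage to accrue 28 additional evaluable patients".

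The analysis set is defined elsewhere. Protocol 8.1.1 says: "All patients treated with FOLFOX or CAPOX and TEMS or TAMIS will be included in the organ preservation rate analysis as primary endpoint". SAP 7.7.1 uses the same set and adds a rate among all chemotherapy-treated patients as an additional result. SAP 2.2 reports: "The trial was closed to further accrual on May 19, 2020 after 58 patients were accrued".

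Protocol 2.0 gives another criterion: the trial succeeds if more than 65% of treated patients have rectum-sparing surgery.

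**The concern.** A bare count is a valid test only at the sample size for which it was derived. Here that size is itself partly an outcome: under Protocol 7.3, patients with progression or no response on the pre-excision assessment go to TME without TEMS or TAMIS, and so are outside the set in 8.1.1. Neither document says what to do if the set is not 50. SAP 7.7.1 adds only a 95% confidence interval.

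This is the go/no-go rule for the primary endpoint. With fewer than 50 evaluable patients the fixed count costs power; with more than 50 it lets a 50% strategy pass more often than planned. A result of 30, 31 or 32 out of 50 (60% to 64%) would be read in opposite ways under 13.3 and 2.0.

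**Working it through.** **Inputs.** From Protocol 13.3: p0 = 0.50, p1 = 0.65, first stage n1 = 22 with stopping at 10 or fewer, final N = 50, cut-off c = 30, loss 15%, accrual 58.

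**Formula.** P(success) = sum over x = 11 to 22 of Bin(x; 22, p) × P[Bin(N − 22, p) ≥ c − x]. At p = 0.50 this is the type I error (alpha); at p = 0.65 it is the power.

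**The plan's own figures.** N = 50, c = 30 gives alpha 0.0977 and power 0.8022. Early stopping under H0 is P[Bin(22, 0.5) ≤ 10] = 0.416. These agree with the stated 0.1, 0.8 and 42%. A search over two-stage minimax designs returns the same design.

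**Other N.** The middle column holds c at 30. The last two take the smallest c with exact alpha ≤ 0.10, leaving stage 1 unchanged.

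| N | alpha / power, c = 30 | smallest valid c | alpha / power at that c |
|---|---|---|---|
| 43 | 0.007 / 0.315 | 27 | 0.063 / 0.680 |
| 45 | 0.018 / 0.475 | 28 | 0.067 / 0.707 |
| 48 | 0.055 / 0.695 | 29 | 0.094 / 0.785 |
| 49 | 0.074 / 0.753 | 30 | 0.074 / 0.753 |
| 50 | 0.098 / 0.802 | 30 | 0.098 / 0.802 |
| 51 | 0.125 / 0.842 | 31 | 0.078 / 0.773 |
| 54 | 0.223 / 0.914 | 33 | 0.065 / 0.763 |
| 57 | 0.330 / 0.941 | 34 | 0.088 / 0.822 |
| 58 | 0.364 / 0.946 | 35 | 0.071 / 0.798 |

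With c = 30, alpha and power both rise with N. Alpha first exceeds 0.10 at 51 and power first reaches 0.80 at 50, so only N = 50 meets both.

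**How likely is 50?** The realised N is not in the documents. The plan's allowance gives 58 × 0.85 = 49.3. As an assumption, let each of 58 patients leave the set independently with probability t, so that N ~ Bin(58, 1 − t). At t = 0.15, P(N = 50) = 0.145, P(N = 49 or 50) = 0.288, P(N < 49) = 0.370 and P(N > 50) = 0.343. Averaged over N:

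| t | alpha / power, c = 30 | alpha / power, c by N |
|---|---|---|
| 10% | 0.168 / 0.859 | 0.076 / 0.775 |
| 15% | 0.094 / 0.739 | 0.080 / 0.765 |
| 20% | 0.045 / 0.565 | 0.079 / 0.743 |

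**Section 2.0.** More than 65% of 50 is more than 32.5, so at least 33. At N = 50, c = 33 gives alpha 0.016 and power 0.505.

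**Stage 1.** SAP 2.2 reports 11 successes among 19 patients. Since 11 already exceeds 10, the decision to continue could not have changed at 22, and the bound of 10 in 22 is kept in the calculations above.

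**The case against.** At the plan's own 15% loss the fixed count keeps average alpha below 0.10, and a cut-off that varies with N gains only 0.765 − 0.739 = 0.026 in power. That stands, and it means the extreme rows of the table should not be taken as the expected case. But the average hides what happens at the N actually obtained, and small departures from 15% move it: alpha is 0.168 at 10% loss and power 0.565 at 20%.

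Protocol 13.3 gives 50 as the maximum, so one could analyse only the first 50 evaluable patients. The documents state no such cap. With one, fixed 30 gives 0.093/0.790, 0.072/0.715 and 0.041/0.560 at 10%, 15% and 20% loss: alpha is safe, but power is no better.

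Three stronger readings are tempting and are not supported:

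- A reader might take the rule literally as 30 of 58 accrued, with alpha about 0.36. Both documents size the design in evaluable patients, and 8.1.1 defines who is evaluable for this endpoint. What remains is a loose word.
- A reader might infer that a patient who declines a recommended TME (a category in SAP 7.5.5) counts as a success under 13.3. But H0 there is set on the protocol-specified organ preservation rate, which 13.2 defines to include ypT0/T1good N0. The count sentence is shorthand; only 8.3 gives a truly shorter definition.
- A reader might conclude that the trial will be judged at 33 of 50. Section 2.0 is background and may loosely restate H1, and 13.3 and SAP 5 agree on 30. It is still worded as a success criterion and contradicts them.

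A cut-off that depends on N also falls as more patients go straight to TME: 27 of 44 passes, yet is 27/58 = 46.6% if all 58 were treated. This follows from the plan's choice of primary set, and it is why the all-chemotherapy rate belongs beside the result.

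**Conclusion.** The design is sound at 50 evaluable patients. The defects are that no cut-off exists for any other number and that section 2.0 states a conflicting threshold. The first is an omission, the second a contradiction, and both should be fixed before the final analysis.

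At the plan's own loss rate the expected harm is lost power (0.739 against 0.80), not inflated alpha. Inflation arises only if more than 50 patients are analysed. These averages assume independent losses from 58 patients; the table values at each N do not need that assumption. All values assume that the 22-patient stage 1 bound applies to the evaluable set. The SAP does not say whether the 19 patients in its interim count belong to that set.

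**What to change.** In Protocol 13.3 and SAP section 5:

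- Replace the reference to all accrued patients with evaluable patients as defined in 8.1.1 and SAP 7.7.1, and use the 13.2 numerator (ypT0/T1good N0 and no radical surgery).
- State that 30 applies at N = 49 or 50. At any other realised N the cut-off is the smallest count with exact two-stage alpha ≤ 0.10, keeping 10 of 22 at stage 1: 27 at 43–44, 28 at 45–46, 29 at 47–48, 31 at 51, 32 at 52–53, 33 at 54–55, 34 at 56–57, 35 at 58. Report attained alpha and power.
- State that the primary-set result alone is the formal decision. Beside it, report the already planned all-chemotherapy-treated rate with its exact 95% confidence interval as a descriptive check, noting that the primary set excludes patients sent straight to TME. Give it no pass/fail cut-off, because two cut-offs could give split verdicts.

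Correct section 2.0 so that 65% is the H1 rate and not the cut-off, and align 8.3 with 13.2.

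Cost: no extra patients or data. Attained power is often below 0.80: 0.680 at N = 43, 0.743 at 44, and 0.707 to 0.822 over 45–58. Accrual has closed, so the change must be dated before outcome data are analysed. The SAP still places that analysis in the future ("A final analysis will be performed on a database which will be locked after all patients completed their treatments"), but the documents cannot show what has since been seen.
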